#### 9.11 Analysis Plan for Secondary Objectives

Both unadjusted comparisons and adjusted comparisons between UC and SHUTi will be performed for secondary outcomes. Safety assessments will be performed using the safety dataset.

#### 9.12 Interim Analysis

No interim analysis will be performed.

#### 9.13 Subgroup Analysis

No subgroup analyses are planned.

#### 9.14 Missing Data

Multiple imputations will be adopted to account for missing data. If differential missing patterns are observed, sensitivity analyses will be performed to evaluate the consequences of potential missing mechanisms.

#### 9.15 Data Management

A comprehensive web-based data management system will be developed for this study using REDCap by the study team which will allow controlled entry through the internet. REDCap provides a secure, web-based environment that provides an intuitive data entry interface and has real-time validation rules (with automated data type and range checks). The system offers easy data manipulation with logged auditing, functionality for reporting, monitoring and querying subject records.

A unique identifier will be assigned to each study participant and their associated study specimens. Patient identifiers will be located only within the subject's study file in a separate, locked cabinet within the Infectious Diseases Research Clinic. Hardcopies of laboratory source records will also be stored in a locked file cabinet. All entryways to the IDRC are secured by padkey codes. Initial screening, consenting of potential subjects, and data abstraction and recording will be completed by either the primary investigators or by the research study coordinators from the IDRC.

## 10.0 HUMAN PARTICIPANTS RESEARCH AND PROTECTION

### 10.1 General Considerations/Investigator Training

The Human Participants Research outlined in this proposal meets the definition of a Phase II clinical trial for the purpose of identifying biological and physiological mechanisms of human disease (not for identifying the superiority of one agent over the other). Therefore, a formal Data and Safety Monitoring Board is not required, although appropriate monitoring through the Data and Safety Monitoring Plan with independent monitor as described below will be fully implemented. This trial will be posted on ClinicalTrials.gov and updated regularly as needed for protocol updates and results. All Indiana University personnel involved with this application have successfully completed the training and examination involved with the Collaborative Institutional Training Initiative Course.

### 10.2 Risks to the Participants

#### 10.2.1 Human Participants Involvement and Characteristics

- Up to 55 HIV-infected participants will be recruited, screened, and consented to participate in these studies. 32 of these will participate and be randomized in the Study I pilot trial investigating the efficacy of cognitive behavioral therapy using the SHUTi computer program to improve insomnia. Another 12 without insomnia will be included in Study II for comparison to the 32 Study I participants.
  - Participants must be at least 18 years of age, have documented HIV infection, and have an HIV-1 RNA level <75 copies/mL while on ART for at least three months. To be in Study I, they must have a screening ISI score  $\geq 11$ ; to be in Study II, they must have a screening ISI score <11.
  - The chief exclusion criteria include known CVD, congestive heart failure, treatment for malignancy (besides localized skin cancers) within 6 months of screening, pro-inflammatory conditions besides HIV infection (e.g. autoimmune diseases, but allowing hepatitis B or C co-infection).
    - Potential participants will be recruited from the HIV outpatient clinics of Indiana University Health Hospitals and Eskenazi Health Hospital.

### 10.2.2 Sources of Materials

- All data for this study will be obtained only after written, informed consent is provided by each participant. Existing medical records will be reviewed for demographics, medical diagnoses, and medications. Questionnaires/surveys to assess insomnia, depression, tobacco use, alcohol use, substance use, physical activity, anxiety, positive/negative affects, and sleep quality/history/beliefs will also be implemented. Measurements of frailty and cognitive functioning will also be performed.
- Results from pertinent medical records and procedures performed for these studies, as outlined above, will be recorded on the human participants involved in the projects in this application.
- Data will be stored in a password-protected computerized database via REDCap that will include only the participants' study identification number (names and other identifiable information will not be included). Therefore, the SID# will be the only link to the participant. Only the principal investigators, co-investigators, and research personnel who will directly obtain the necessary data will have access to the participant identities. All data obtained for this study will be obtained only after written, informed consent is provided by each participant.
- Records will be reviewed manually. SHUTi treatments and questionnaires will be completed in private settings. These data will be collected solely for the purpose of the proposed research projects.

### 10.2.3 Potential Risks

- There are minimal risks to the participants enrolled in the proposed research. There is the potential loss of participant confidentiality. There are no known risks related to the implementation of the SHUTi cognitive behavioral therapy program. Participants may feel unease in completing the questionnaires. There may be some muscle soreness and a very minor theoretical risk of falls when performing the physical functioning assessments.
- The study team is trained to perform these assessments in order to minimize these potential risks. Of note, no falls have occurred to date when performing these assessments.
- The principal alternative to these procedures would be not to participate in the research.

## 10.3 Adequacy of Protection Against Risks

### 10.3.1 Recruitment and Informed Consent

- Recruitment will only begin once the Indiana University Institutional Review Board has approved this study. All participants will be recruited from the outpatient HIV care clinics at Indiana University Health Hospitals and Eskenazi Health Hospital. Self-referrals from other venues will also be considered. If the primary caregiver for the patient believes he or she is eligible for the study and allows the patient to be approached for screening, one of the study investigators or a study nurse will approach each potential participant during his or her regularly scheduled clinic visit or by phone if the patient is not present in clinic. If eligibility is confirmed, then the purpose, procedures, and risks and benefits of the study will be discussed with the participant. Participants will have ample opportunity to ask questions and to have all concerns addressed. If the participant wishes to pursue screening, then written informed consent will be obtained (and a copy given to the participant). All consent forms will be stored in a locked file cabinet.

### 10.3.2 Protection Against Risk

10.3.2.1 Confidentiality. To minimize the risk to participant confidentiality, patient identifiers will be removed once his or her data is abstracted and recorded, and only the random study identification number (generated when consent is provided) will be used. All hardcopy study data will be kept in a secured and locked file cabinet. All electronic data will be kept in a password-protected computer database. The only link between patient identifiers and the randomized study identification number will be kept in separate files. Identifiers will never be used in the analysis or presentation of study results.

Information collected from the participant for this research may be used for future research studies or shared with other researchers for future research. If this happens, information which could identify the participant will be removed before any information are shared. Since identifying information will be removed, we cannot ask for your additional consent.

10.3.2.2 Questionnaires. Participants may feel uneasy or discomfort in completing the depression, treatment adherence, and physical activity questionnaires. To minimize this risk, questionnaires will be completed in private settings with any questions regarding completion of the questionnaires addressed by trained study team psychology personnel.

10.3.2.3 Suicidal ideation and management. Although not an inherent risk of the study intervention or study procedures, participants may have depression as determined through completion of the PHQ-9 questionnaire. As such, these participants may have suicidal ideation at screening or develop suicidal ideation during the course of the study. We have already put into place a protection protocol for just this event in our previous studies in HIV-uninfected depressed patients (please see Appendix at end of this protocol). If a participant reports having thoughts of being better off dead or of hurting him/herself (i.e., responds with a 1, 2, or 3 to PHQ-9 Item #9 or spontaneously reports suicidal ideation), the visit will be immediately stopped, and the research assistant will interview the participant to complete the Patient Suicidality Form (see Appendix). If the participant answers “no” to all three suicide questions or if the patient answers “yes” only to Question 3 (previous attempt) and the most recent attempt was  $\geq 10$  years ago, the visit will proceed as normal, and the completed Patient Suicidality Form will be given to the principal investigator.

If the participant answers “yes” to any of the three questions (for Question #3 the previous attempt must be within the past 10 years), the research assistant will immediately contact the principal investigators. [name] (a clinical psychologist) and [name] (a physician) will review the case as soon as possible, but no later than the same day, to determine the appropriate course of action (e.g., immediately contact the patient’s primary care provider, primary HIV provider, clinical social worker, or care coordinator, consult with clinicians at Midtown Community Mental Health Center, and/or escort the patient to the Crisis Intervention Unit at Eskenazi Health). Additional authorities, including the police, may be contacted if immediate harm is of concern. Participants may be withdrawn from the study.

A letter, both an email and a hard copy version, will also be sent to the potential participant's primary provider notifying him/her of the situation (see below).

If an enrolled participant reports having thoughts of being better off dead or of hurting him/herself during any telephone calls (e.g., a scheduling call or a call to the study team initiated by the participant), the exact same process as outlined above will be initiated. Please see the Appendix for the full Suicide Management Plan.

10.3.2.4 Adverse event financial management, grading, and reporting. In the event of an adverse event, necessary medical and professional intervention will be provided immediately and billed to the participant's medical insurance (if available). If the participant does not have insurance, care will be provided via the indigent care program at Eskenazi Health Hospital. Standard procedures for reporting deviations from protocols will be followed; serious adverse events that meet the Indiana University IRB prompt reporting requirements will be reported within 10 business days. All adverse events will be graded using The Division of AIDS Table for Grading Adult Adverse Experiences is located at: <http://roc.s-3.com/members/download/adulttox.pdf>.

10.3.2.5 Data and Safety Monitoring. [name] of the Division of Infectious Diseases, Indiana University will serve as the independent chair and monitor for this trial. She will receive reports at least every six months regarding the progress and participant safety during the trial.

#### 10.4 Potential Benefits of the Proposed Research to the Participants and Others

- Potential benefits to the participants include an evaluation of their insomnia, depression, functional capacity, and frailty status. They may also derive short-term benefits from the SHUTI insomnia treatment program, although this is not guaranteed. Finally, the participants may also benefit from knowing that their participation will accrue knowledge that could benefit other HIV-infected patients.
- Although there are no guaranteed clinical benefits from those who are randomized to treatment with SHUTi, this program appears quite safe when used in HIV-uninfected participants. The standard of care will not be altered in the control participants. Therefore, the ancillary benefits to the participants in the proposed studies significantly outweigh the minimal risks in this study. Moreover, the proposed research may lead to other prevention and therapeutic studies that would eventually demonstrate how to reduce inflammation and improve endothelial function, which consequently may reduce future cardiovascular events in the HIV-infected population, and to improve frailty and functional status in the aging HIV population. This would benefit society directly by impacting clinical practice.

#### 10.5 Importance of the Knowledge to be Gained

- The knowledge that will be gained from this study will determine the relationships between HIV, insomnia, functional capacity, and frailty. This would potentially impact the clinical care of HIV-infected patients at risk for worse long-term outcomes. Furthermore, prevention and therapeutic strategies for these highly prevalent diseases can then be formulated, thereby reducing morbidity, mortality, and cost to the patients and society in general.
- Again, the risks to the participants are considered minimal. Even if the results are negative, the results of these investigations will add substantially to our knowledge on effects of an internet-based cognitive behavioral program on insomnia in virologically-suppressed, HIV-infected persons. Therefore, the importance of the knowledge gained outweighs the risks to the participants.

#### 10.6 Data and Safety Monitoring Plan

- Progress of these studies, including data monitoring, participant enrollment, protocol deviations, and all SAE, will be reviewed by a panel including the PIs (Drs. [name] and [name]) and an HIV expert investigator at Indiana University not directly connected with this study ([name] of the Division of Infectious Diseases, Indiana University School of Medicine). Reports, which will include descriptions of all adverse events, will be prepared for review by this panel every 12 months. Any study participant prematurely discontinued due to an adverse event will be reviewed immediately. Standard procedures for reporting deviations from protocols to the Indiana University ICRC, IRB, and NHLBI will be implemented. Serious Adverse Events (SAEs) will also be reported to the IRB within 30 working days and subsequently forwarded to NHLBI as required.

## 10.7 Inclusion of Women and Minorities

There are no exclusion criteria based on gender, racial category, or ethnicity. Based on our previous cumulative experience and the general HIV-infected population cared for at the study sites at the Indiana University Health Medical Center (Eskenazi Hospital, Methodist Hospital, VA Roudebush Hospital, and Indiana University Health Hospital), it is anticipated that approximately 25% of the study participants will be women.

It is also anticipated that approximately 50% and 10% of the study participants will be black and Hispanic, respectively. American Indians, Alaskan Natives, Asians, Native Hawaiians or Other Pacific Islanders are not expected to be represented in the proposed study population due to extremely low representation of these groups within the Indiana University Health Hospitals HIV outpatient clinics and in Indianapolis in general.

## 10.8 Inclusion of Children

Subjects over the age of 18 will be eligible for enrollment. However, participants under age 18 will be excluded to minimize confounding from developmental changes that may affect the studies' endpoints of behavioral and functional measures.

## Appendix: Suicide Management Plan

Suicide management plans very similar to the one described below have previously been approved by the Indiana University IRB and were successfully implemented in the two other depression trials conducted by our team (IRB #'s 1105005448 and 1110007119). Those suicide management plans were constructed with input from Eskenazi Midtown Community Mental Health Center leadership ([name], Associate Vice President, and [name]), who concluded that the plans provide a high level of protection while minimizing disruption to usual clinical activities. In the present trial, we will assess suicidal ideation at every study visit, and we are prepared to appropriately handle the situation should one of the enrolled patients exhibit suicidal ideation.

### (a) In-Person Study Visits

Suicidal ideation will be assessed using Item #9 of the PHQ-9 at the Screening Visit and all Main Study Visits (see Section 6.1). If a participant reports having thoughts of being better off dead or of hurting him/herself (i.e., responds with a 1, 2, or 3 to PHQ-9 Item #9 or spontaneously reports suicidal ideation) during any of the Study Visits, the visit will be immediately stopped, and the study coordinators running these visits will interview the participant to complete the Patient Suicidality Form (see below). If the potential participant answers “no” to the clarifying question, the visit will proceed as normal. If the potential participant answers “yes” to the clarifying question, the participant will be asked the three suicide questions. If this interview is required at one of the Weekly SHUTi Sessions, the graduate student research assistants will perform this interview, as they will conduct these treatment sessions.

The study coordinators have been trained by [name], a clinical psychologist, in conducting the interview to complete the Patient Suicidality Form and in following this protocol. [name] will also serve as the primary supervisor to these study coordinators when it comes to their tasks related to this suicide management plan. In [name] completed (IRB #'s 1105005448 and 1110007119) and ongoing (IRB # 1411802537) clinical trials, he has trained ResNet research assistants to effectively conduct this interview and provide a high degree of protection to patients.

The graduate student research assistants are doctoral students enrolled full-time in IUPUI's clinical psychology Ph.D. program, which is accredited by the American Psychological Association and of which [name] is a core member. The research assistants have completed graduate coursework in psychological assessment, psychological interventions, psychopathology, and ethics and have acquired supervised clinical experience in local healthcare settings. The graduate student research assistants have also been trained by [name] in conducting the interview to complete the Patient Suicidality Form and in following this protocol. [name] is also the primary supervisor of graduate student research assistants.

It is worth noting that neither the study coordinators nor the graduate student research assistants will be making any decisions regarding how to handle a situation. Instead, they will collect information by administering a highly structured, 3-question interview (Patient Suicidality Form, found below) and will follow the straightforward, step-by-step protocol described in the next paragraph. They will be instructed to call [name] if they are unsure about a participant's response to any of the three questions. As he has done in his past depression trials and is described above, [name] will train the study coordinators and the graduate student research assistants in administering the brief interview and in following the protocol. This training will be repeated periodically during the study period.

If the participant answers “no” to all three suicide questions or if the patient answers “yes” only to Question 3 (previous attempt) and the most recent attempt was  $\geq 10$  years ago, the visit will proceed as planned, and the completed Patient Suicidality Form will be given to [name].

If the participant answers “yes” to any of the three questions (for Question #3 the previous attempt must be within the past 10 years), the study coordinators or the graduate student research assistant will immediately stop the visit, will contact Drs. [name] and/or [name], and will stay with the participant until a decision is made. If clinically indicated (e.g., the situation is an emergency), a graduate student research assistant and/or [name] will go to the visit location (Infectious Diseases Research Clinic or ICRC) to assist the study coordinators.

Drs. [name] and/or [name] will review all cases screening positive for suicidal ideation immediately to determine the appropriate course of action – e.g., interview the patient to obtain further information, immediately contact the patient’s HIV provider or clinical social worker to involve them in the decision-making process, consult with clinicians at the Eskenazi Health Midtown Community Mental Health Center to aid in the decision-making process, escort the patient to the Eskenazi Health Crisis Intervention Unit (‘warm handoff’), and/or contact the police if the patient is at imminent danger of harm and is refusing all care. Either [name] or [name] will also call the participant’s HIV provider notifying him/her of the situation if the provider was not involved in the decision-making process. Regardless of the exact course of action, the study team will ensure that the participant is connected to the appropriate existing clinical services. If the patient’s HIV provider no longer believes that the patient is appropriate for this trial following this situation, the patient will be withdrawn from the trial.

Of note, because patients exhibiting active suicidal ideation are not eligible for this trial, we expect that it will be a rare occurrence that an enrolled patient will screen positive for suicidal ideation. Zero enrolled participants in our two prior depression trials have exhibited suicidal ideation during their involvement in the studies.

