### 4.2 Exclusion Criteria

- 4.2.1 Inability to complete written, informed consent.
- 4.2.2 Incarceration at the time of any study visit.
- 4.2.3 Active suicidality, as determined by the patient's HIV provider or social worker following a positive response (1, 2, or 3) to PHQ-9 Item #9 and a positive response (yes) to one or more of the three questions (for Question #3, the previous attempt must be within the past 10 years) on the Patient Suicidality Form (see Appendix).
- 4.2.4 Diagnosed vascular disease (documented history of angina pectoris, coronary disease, peripheral vascular disease, cerebrovascular disease, aortic aneurysm, or otherwise known atherosclerotic disease).
- 4.2.5 History of congestive heart failure, even if currently compensated.
- 4.2.6 Diagnosed disease or process, besides HIV infection, associated with increased systemic inflammation (including, but not limited to, systemic lupus erythematosus, inflammatory bowel diseases, other collagen vascular diseases).

Note: Hepatitis B or C co-infections are NOT exclusionary

- 4.2.7 Known or suspected malignancy requiring systemic treatment within 180 days of the Entry Visit.

NOTE: Localized treatment for skin cancers is not exclusionary.

- 4.2.8 Therapy for serious medical illnesses within 14 days prior to screening.

Note: Therapy for serious medical illnesses that overlaps with a main study visit will result in postponement of that study visit until the course of therapy is completed; postponement outside of the allowed study visit timeframe will result in study discontinuation.

- 4.2.9 Pregnancy or breastfeeding during the course of the study.

- 4.2.10 Receipt of investigational agents, cytotoxic chemotherapy, systemic glucocorticoids (of any dose), or anabolic steroids at the Entry Visit.

Note: Physiologic testosterone replacement therapy or topical steroids is not exclusionary. Inhaled/nasal steroids are not exclusionary as long as the participant is not also receiving HIV protease inhibitors.

- 4.2.11 Active drug use or dependence that, in the opinion of the investigator, would interfere with adherence to study requirements.

- 4.2.12 History of schizophrenia, bipolar disorder, or dementia.

NOTE: Depression is not exclusionary as long as the severity of depression does not impede ability to perform the required study procedures.

- 4.2.13 Musculoskeletal or neurologic disorders that impede ability to perform the required study procedures.

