### 7.0 ADVERSE EVENT MANAGEMENT

Although not an inherent risk of the study intervention or study procedures, participants for this study may have depression as determined through completion of the PHQ-9 questionnaire. As such, these participants may have suicidal ideation at screening or develop suicidal ideation during the course of the study. We have already put into place a protection protocol for just this event in our ongoing studies in HIV-infected and HIV-uninfected depressed patients (please see Appendix at end of this protocol). If a participant reports having thoughts of being better off dead or of hurting him/herself (i.e., responds with a 1, 2, or 3 to PHQ-9 Item #9 or spontaneously reports suicidal ideation), the visit will be immediately stopped, and the research assistant will interview the participant to complete the Patient Suicidality Form (see Appendix). If the participant answers “no” to all three suicide questions or if the patient answers “yes” only to Question 3 (previous attempt) and the most recent attempt was  $\geq 10$  years ago, the visit will proceed as normal, and the completed Patient Suicidality Form will be given to the principal investigator.

If the participant answers “yes” to any of the three questions (for Question #3 the previous attempt must be within the past 10 years), the research assistant will immediately contact the principal investigators. [name] (a clinical psychologist) and [name] (a physician) will review the case as soon as possible, but no later than the same day, to determine the appropriate course of action (e.g., immediately contact the patient’s primary care provider, primary HIV provider, clinical social worker, or care coordinator, consult with clinicians at Midtown Community Mental Health Center, and/or escort the patient to the Crisis Intervention Unit at Eskenazi Health). Additional authorities, including the police, may be contacted if immediate harm is of concern. Participants may be withdrawn from the study.

A direct correspondence by phone call and letter (both an email and a hard copy version), will also be sent to the potential participant’s primary provider notifying him/her of the situation (see below).

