**Clarifying Question**

***Over the past 2 weeks, have you been having thoughts of hurting yourself in some way?***

Yes \_\_\_\_\_ No \_\_\_\_\_  
(Continue) (Stop)

Comments:

.....

I'm going to ask you a few questions that are part of this study, because we have seen that in some patients with these symptoms, these are important concerns.

1. *Do you have a suicide plan?* Yes \_\_\_\_\_ No \_\_\_\_\_

Comments:

2. *Have you been struggling against thoughts about committing suicide?* Yes \_\_\_\_\_ No \_\_\_\_\_

Comments:

3. *Have you attempted suicide in the past?* Yes \_\_\_\_\_ No \_\_\_\_\_

If YES, in what year was the most recent attempt? \_\_\_\_\_

Comments:

**If the participant answers "yes" to any of the three questions (for Question #3 the previous attempt must be within the past 10 years), you must carefully follow the procedures described in the Suicidal Ideation Protection Protocol.**

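### The suicidality form stops at a no to a clarifying question narrower than its trigger, so answers that exclusion 4.2.3 needs can go uncollected before same-visit randomization

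*Combined protocol and SAP*

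**What the plan says.** The Appendix (Suicide Management Plan, part (a) In-Person Study Visits) states: "Suicidal ideation will be assessed using Item #9 of the PHQ-9". The interview is triggered when a participant "reports having thoughts of being better off dead or of hurting him/herself", meaning a score of 1, 2 or 3 on item 9 or a spontaneous report.

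Part (a) and the Patient Suicidality Form then begin with a clarifying question: "Over the past 2 weeks, have you been having thoughts of hurting yourself in some way". A yes leads to the three suicide questions (a plan, resisting suicidal thoughts, a past attempt). For a no "to the clarifying question, the visit will proceed as normal", and the form is marked to stop.

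Other parts of the plan do not mention this step:

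- Exclusion 4.2.3 rests on a positive item 9 together with "a positive response (yes) to one or more of the three questions", followed by a determination by the HIV provider or social worker. For Question 3 the attempt must fall within the past 10 years.
- Section 7.0 says staff "will interview the participant to complete the Patient Suicidality Form". On a no to all three questions, or a lone yes to Question 3 with an attempt at least 10 years ago, "the visit will proceed as normal, and the completed Patient Suicidality Form will be given to the principal investigator". Section 10.3.2.3 has the same rule.
- A later paragraph of Appendix (a) and the telephone plan in Appendix (b) also word their rules around the three questions, and hand the form to a named member of the team even when all three answers are no.

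**The concern.** The clarifying question is narrower than the event that triggers the form. Someone whose positive item 9 reflects only thoughts of being better off dead can truthfully say no to thoughts of self-harm in the past two weeks. The interview then ends before the questions that the rest of the plan relies on.

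Two things are at stake. The first is eligibility: exclusion 4.2.3 cannot be applied as intended if its defining questions were not asked, and Section 3.4 randomizes Study I participants at the end of the same visit. The second is safety: on this branch no text expressly says that the form goes to anyone.

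**Working it through.** The plan gives no figure to reproduce. The check is a comparison of texts, followed by a count of how often the step could arise.

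**Step 1: trigger against gate.**

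| | Thoughts of being better off dead | Thoughts of hurting oneself |
|---|---|---|
| Trigger (item 9 or spontaneous report) | covered | covered |
| Clarifying question (past two weeks) | not covered | covered |

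A truthful no at the gate is therefore compatible with a positive trigger.

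**Step 2: what lets the visit or call proceed.**

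| Text | Condition for proceeding | Hand-over of form when proceeding |
|---|---|---|
| Section 7.0; Section 10.3.2.3 | No to all three, or only Question 3 yes with an attempt at least 10 years ago | Principal investigator |
| Appendix (a), later paragraph | Same | Named team member |
| Appendix (b), telephone | No to all three | Named team member |
| Appendix (a), opening paragraph; the form | No to the clarifying question | None stated |

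**Step 3: trace one case (hypothetical).** At Entry a participant reports only thoughts of being better off dead and attempted suicide two years ago.

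- If the three questions are asked, "Have you attempted suicide in the past" draws a yes within 10 years. Staff contact the investigators, and 4.2.3 calls for a determination by the HIV provider or social worker.
- If the form stops at the clarifying question, the attempt is never raised, no determination is prompted, and a Study I participant can be randomized that day.

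The Appendix also mentions item 9 at a Screening Visit, but the Schedule of Events (6.1) has no such visit. Its first PHQ-9 is at Entry.

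**Step 4: how often the step could arise.** Inputs are the sample sizes in the Design section, the Schedule of Events, the dropout in Section 9.2 and the consented total in Section 10.2.1.

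- Entry: 32 + 12 = 44 scheduled PHQ-9 administrations.
- Week 10: 32 with full retention, so 44 + 32 = 76.
- With 25% dropout in the trial: 32 × 0.75 = 24 at Week 10, so 44 + 24 = 68.
- If all 55 consented people complete it at Entry: 55 + 32 = 87.

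These are opportunities, not affected people. They are not a ceiling either, since spontaneous reports can arise at up to 16 × 6 = 96 SHUTi sessions and on study calls.

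The share who are positive on item 9 but answer no at the gate is not in the documents. Purely as an assumption:

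| Assumed share | Of 76 scheduled | Of 44 at Entry |
|---|---|---|
| 1% | 0.8 | 0.4 |
| 5% | 3.8 | 2.2 |
| 10% | 7.6 | 4.4 |

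**The case against.** The strongest reply is that the plan has one working procedure, summarised incompletely in places. Sections 7.0 and 10.3.2.3 both end by referring to the Appendix for the full plan. Every route uses the same printed form, so staff will probably meet the clarifying question whichever section sent them there. The later paragraph of Appendix (a) can be read as what happens once the gate has been passed. All of this stands. A reader might infer two rival procedures, with the outcome depending on which page staff follow; the documents do not support that.

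A reader might also infer that nobody reviews a case stopped at the gate. That is not established. Appendix (a) has the investigators review every case that screens positive, and elsewhere assesses ideation by item 9, so review may be intended. The text does not settle it: a positive screen is not defined, the sentence follows the paragraph on a yes to the three questions, and immediate review fits poorly with a visit that simply continues.

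The gate may be deliberate triage. It is labelled as clarifying and has printed routing, and the Appendix says very similar plans were approved and used in two earlier trials. It does not say whether those plans had this gate. The possibility stands, and the fix allows for it.

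It can also be said that 4.2.3 remains determinate, since without a yes the criterion is not met. That is formally right, but it is unmet only because the question was not put. Recent self-harm thoughts and a past attempt are different facts, so the gate cannot stand in for Question 3.

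Finally, the Appendix reports no suicidal ideation among enrolled participants in two earlier depression trials. That suggests rarity after enrolment, but it does not describe people at the eligibility step.

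**Conclusion.** The point holds as a gap in the form and its routing. Followed as written, the form can let a participant with a positive item 9 and a recent attempt reach same-visit randomization without the answers that exclusion 4.2.3 uses. It also leaves the hand-over on the no branch unstated. The conclusion rests on staff administering the form as printed, and on item 9 covering better-off-dead thoughts as the plan describes it.

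Severity is minor, and the change is a cheap improvement. The number affected is unknown and may be zero; the shares above are assumptions. The primary endpoint, the analysis and the sample size are untouched. Whether passive thoughts with a past attempt amount to active suicidality is a clinical judgement. The point is only that the information should be there for whoever makes it.

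**What to change.** **Preferred change.**

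- On the form, change the no routing from stop to continue.
- In the opening paragraph of Appendix (a), replace the two sentences on the clarifying question with: *The clarifying answer will be recorded. Whatever it is, all three suicide questions will be asked after any positive item 9 or spontaneous report, and every form will be given to the supervising psychologist or principal investigator the same day.*
- In the review paragraph of Appendix (a), state that a positive item 9 or a spontaneous report counts as a positive screen for the same-day hand-over. Immediate review stays reserved for a yes to any of the three questions (for Question 3, an attempt within the past 10 years).
- Add the same-day timing to the existing hand-over in Sections 7.0 and 10.3.2.3, the later paragraph of Appendix (a), and Appendix (b).

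**Minimum, if the sponsor confirms that the gate is deliberate.** Widen the clarifying question to include thoughts of being better off dead, require same-day hand-over after a no, and state the gate in 4.2.3, 7.0, 10.3.2.3, the later paragraph of Appendix (a), and Appendix (b).

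**Cost.** Up to three more questions and a form hand-over for a few participants, and an occasional extra interrupted visit. There may also be an occasional extra determination under 4.2.3, which could exclude someone who would otherwise enrol. A short IRB amendment and brief retraining are needed.
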